3.2 Analysis Populations

For each of the primary and secondary objectives, we will define an intention-to-treat analysis (ITT) population as the population of all GPs who underwent randomization, regardless of participation in the educational session at Ti and loss to follow-up.

For each of the primary and secondary objectives, a per-protocol analysis (PPA) population will include all GPs who participated in the educational session at Ti.

Handling of missing data in the ITT and PPA populations is described in section 4.3.

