4.3 Missing Data

Missing data may potentially occur on two levels:

- GPs: baseline (including demographic) characteristics, failure to undergo the intervention, failure to return CRFs (including loss to follow-up) or questionnaires.
- Patients (data from the CRFs): demographic characteristics, type of vaccination.

To analyze the study objectives, we will use the following procedures to handle missingness in the ITT and PPA population data sets:

- Loss to follow-up of GPs: complete-case analysis.
- Missing baseline characteristics of GPs and missing patient-level characteristics: complete-case analysis.

For each study objective, we will conduct a sensitivity analysis on the IIT population using multilevel chained equations-based multiple imputation with 5 datasets and 20 iterations. We will restrict use of multiple imputation to this sensitivity analysis and use a complete-case approach for the main analysis due to the low anticipated drop-out rates (2).

For other analyses not belonging to a study objective, we will handle missing data by pairwise deletion (i.e., by omitting only cases with missing values of variables relevant to the current analysis).

The nature and frequency of missing data will be reported for all analyses. Differences in loss to followup frequencies between the study arms will be assessed using Pearson's chi-squared and Fisher's exact test.

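### Five imputed datasets are too few for a stable p-value in the only sensitivity analysis that covers GPs lost to follow-up, and its imputation predictors are not fixed

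*SAP*

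**What the plan says.** Section 3.2 defines the ITT population as "the population of all GPs who underwent randomization, regardless of participation in the educational session at Ti and loss to follow-up". The per-protocol set consists of the attenders: "a per-protocol analysis (PPA) population will include all GPs who participated in the educational session at Ti".

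Section 4.3 names, at GP level, these sources of missing data: "baseline (including demographic) characteristics, failure to undergo the intervention, failure to return CRFs (including loss to follow-up) or questionnaires". Its handling rules cover two cases, both by complete-case analysis: GPs lost to follow-up ("Loss to follow-up of GPs: complete-case analysis") and missing GP or patient characteristics. Failure to undergo the intervention has no rule of its own.

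For each objective, one sensitivity analysis on the ITT population is planned: "multilevel chained equations-based multiple imputation with 5 datasets and 20 iterations". Imputation is confined to this analysis, on the ground that drop-out is expected to be low; the SAP gives no figure. It states no imputation variables, no seed and no analysis under a different assumption about the missing counts. Section 4.2.5 refers to 4.3 for missing-data sensitivity analyses and adds none.

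**The concern.** The main analysis leaves out lost GPs, whom section 3.2 counts as members of the ITT population. Imputation is the one step that puts them back, so its value lies in showing whether the complete-case result survives. Two features weaken it.

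- **Too few datasets.** With five imputations the pooled estimate and its p-value shift noticeably when the same code is re-run with another seed. Section 6 reports p-values to three decimals, which is finer than five datasets can support near 0.05.
- **Open predictors.** Standard chained equations fill a missing count from GPs who resemble the missing one on the variables in the imputation model. If these are study arm and the covariates of the primary model, imputation largely returns the complete-case estimate plus simulation noise. Agreement between the two would then say little about selective loss. If attendance is left out, an active-arm GP with no session and no counts is treated as a trained one.

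**Working it through.** The SAP does not derive the number 5 and gives no drop-out rate, so there is no figure of its own to reproduce.

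**Inputs**
- M = 5 imputed datasets (section 4.3).
- Fraction of missing information, FMI: assumed 10% to 20%, with 5% as a lower case.
- Significance level 0.05 and two-sided 95% intervals (section 3.1).
- For the stress test only: 14.9/9.5 from section 2.4, used as an illustrative rate ratio. This is an assumption, because those figures are coverage changes and not count rates.

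**Step 1: Monte Carlo error.** The between-imputation variance is FMI × total variance, and the part due to finite M is that divided by M. In units of the standard error, the Monte Carlo SD is √(FMI/M).

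| FMI | M = 5 | M = 50 |
|---|---|---|
| 5% | √(0.05/5) = 0.100 | 0.032 |
| 10% | √(0.10/5) = 0.141 | 0.045 |
| 20% | √(0.20/5) = 0.200 | 0.063 |

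The relative efficiency, 1/(1 + FMI/M), is already 99%, 98% and 96% at M = 5. The weakness is therefore in reproducibility of the p-value, not in precision.

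**Step 2: p-value from seed to seed.** A hand calculation uses the two-sided normal p at 1.96 ± 1.96 × SD. At M = 5 it gives 0.025 to 0.092 (FMI 10%) and 0.019 to 0.117 (FMI 20%). It ignores that the between-imputation variance is itself estimated from five values. Simulation with Rubin's rules, Barnard-Rubin degrees of freedom and large complete-data degrees of freedom gives these 95% ranges:

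| p with unlimited M | FMI | M = 5 | M = 50 |
|---|---|---|---|
| 0.050 | 5% | 0.031–0.083 | 0.043–0.058 |
| 0.050 | 10% | 0.024–0.107 | 0.040–0.063 |
| 0.050 | 20% | 0.016–0.153 | 0.035–0.070 |
| 0.036 | 10% | 0.017–0.082 | 0.028–0.046 |
| 0.036 | 20% | 0.011–0.124 | 0.025–0.052 |
| 0.012 | 10% | 0.005–0.036 | 0.009–0.017 |
| 0.012 | 20% | 0.003–0.065 | 0.008–0.020 |

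The row at 0.050 is the worst case; a p-value exactly on the threshold crosses it at any M. The rows at 0.036 show the practical gain. With five datasets about 75% (FMI 10%) or 63% (FMI 20%) of seeds give p below 0.05; with 50 datasets the shares are above 99% and about 96%. At 0.012 and FMI 10%, five datasets already give the same conclusion in more than 99% of seeds.

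**Step 3: what a control-based version could show.** Let d be the share of active-arm GPs whose counts are missing, with rate ratio R = 14.9/9.5 = 1.57 among the others. Filling the missing ones at the control rate gives (1 − d)R + d.
- d = 5%: 1.54, log effect smaller by 4%.
- d = 10%: 1.51, smaller by 8%.
- d = 20%: 1.46, smaller by 17%.

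Imputation from trained same-arm colleagues would leave R at 1.57. The gap between the two is how far the result depends on what is assumed about the missing GPs.

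**The case against.** The best defence is that no decision rests on the imputed result. Section 4.2.3 ties rejection of the null to the study-arm estimate in the final model, which section 4.3 fits to complete cases. A reader might infer that the trial's p-value depends on a random seed. It does not: the primary p-value involves no imputation. This stands, and it makes the point a modest one.

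A reader might also infer that untrained active-arm GPs are filled in as if trained. The SAP does not say so. A non-attender who returns CRFs keeps the observed counts in the ITT analysis. Only GPs without counts are imputed, and whether they are treated as trained depends on an imputation model that the SAP leaves open. Missing-at-random is likewise inferred from the method and is not written in the text.

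Nor does section 3.2 conflict with such imputation. It defines who belongs to the population ("regardless of participation in the educational session at Ti and loss to follow-up") and refers missing data to 4.3; it sets no imputation assumption.

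Finally, the plan has other safeguards. It reports the nature and frequency of missing data, tests loss between arms, compares lost GPs with the ITT population (section 4.2.1) and repeats the objective analyses on attenders. These help to detect selective loss, but none shows how the estimate would move if the lost GPs differed from those observed.

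**Conclusion.** The point holds in limited form. Five datasets leave a Monte Carlo error of about 14% to 20% of the standard error at an assumed FMI of 10% to 20%, enough to put a borderline sensitivity p-value on either side of 0.05. Further from 0.05 and with low drop-out, the conclusion rarely changes. The trial's primary conclusion is not at risk from this.

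That the imputation would largely reproduce the complete-case result, with absent non-attenders filled from trained colleagues, is conditional on a model that has arm but not attendance. The SAP neither states nor excludes that model.

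It would go too far to read the 4% to 17% in Step 3 as a bias in the plan. Those figures assume that every active-arm GP without counts gained nothing. A GP lost after the session was trained, and imputing that GP from trained colleagues may be reasonable. The documents do not say how many GPs would lack both session and counts. The control-based run is therefore a useful stress test and not the correction of a demonstrated error.

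**What to change.** In section 4.3:

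1. Replace 5 datasets by at least 50, fix the seed in advance, and report the Monte Carlo error of the pooled estimate.
2. List the imputation predictors and include study arm and session attendance. Attendance can inform the imputation only if some non-attenders return counts, so report how many do, by arm.
3. For the primary objective, add one control-based imputation in which missing counts of active-arm GPs are drawn from the control-arm rate given baseline category and workload. Show it next to the standard version, labelled as deliberately conservative because it also treats GPs who were trained and then lost as having gained nothing.

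The cost is some computing time, a few sentences and one extra table row. Data collection and the primary analysis stay as they are.

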4.4 Data Management

The received paper clinical report forms (CRFs) will be handled as source data. Data concerning administered HPVv doses will be transcribed from the paper CRF to a digital database using the software OpenClinica version 3.11 (OpenClinica LLC and collaborators, Waltham, MA, USA, www.Open-Clinica.com). OpenClinica is a well-established and GCP-conform clinical data management system. An audit trail is available within the software.

The study nurse will transcribe data from the pen-and-paper CRFs, baseline and follow-up questionnaires into OpenClinica. Another member of the study team will validate all transcribed data manually, and a further member of the study team will conduct sample checks. OpenClinica will run on a separate computer with no network connection (due to security reasons) located in the Institute of Primary Care of the University of Zurich. To gain access to the software and to the data a password will be needed and available to selected members of the study team only. All users of the software will be granted specific rights (for example, the study nurse will be allowed to enter data but not to edit or export it). The study statistician will not be granted access to OpenClinica. Backups of the data will be stored on a computer connected to the network of the University Hospital Zurich. A member of the study team will provide the statistician with anonymized data exports from Open-Clinica in form of comma-separated values files and Excel spreadsheets (Microsoft Excel, Microsoft Corporation, Redmond, WA, USA, https://office.microsoft.com/excel) after blinding for the study arm.

4.5 Statistical Software

Statistical analysis will be performed with the software R version 4.1.0 or higher (R Foundation for Statistical Computing, Vienna, Austria) (8).

5 Safety Analyses

This study will include no safety analyses, since no safety data collection will be required (2).

6 Reporting Conventions

For summary statistics, we will use one decimal place more than for the data from which they originate. We will make exceptions were deemed appropriate, such as for reporting of extremal values, where we will use the same number of decimal places as for the data from which they originate.

We will report quantities derived from regression models (coefficient estimates with confidence intervals and variance estimates) and values of test statistics up to three decimal places. We will report p-values of at least 0.001 up to three decimal places, and p-values smaller than 0.001 as "< 0.001".

7 Summary of Changes to the Protocol

The following points needed changes with respect to indications in the study protocol:

- Included GPs will not be asked for a precise number of administered vaccinations during Pb, but will provide a categorical estimate.
- Accordingly, the primary and secondary outcomes will not compare changes from T0 to the respective time points, but will assess the absolute HPVv uptake between T0 and the respective time points.
- Duration of Pb will be reduced from 6 months to 3 months due to practicability reasons.
- Accordingly, to ensure comparability with HPVv numbers during the baseline period, the measurements at 2 and 4 months after T0 will be replaced by one single measurement at 3 months after T0.

References

1. Grischott T. The Shiny Balancer – software and imbalance criteria for optimally balanced treatment allocation in small RCTs and cRCTs. BMC Med Res Methodol 2018; 18(1):108.

2. [name]. Impact of a multifaceted, targeted intervention on the HPV vaccination rate in Swiss Primary Care: A cluster randomized controlled study (Study protocol version 1.0). 2021.

